5.4 Conventions

5.4.1 Descriptive Statistics

Descriptive statistics (the number of subjects [n], mean, standard deviation [SD], median, minimum, maximum, and not reported) will be used to summarize continuous variables. Means will be presented to one more decimal place than the recorded data. Medians will be presented using the same number of decimal places as the recorded data unless the calculated median results in an additional decimal place ending in “5” (i.e. 5 & 7 = 6, 5 & 8 = 6.5, etc.). Standard deviations will be presented to two more decimal places than the recorded data. Minimum and maximum values will be presented using the same number of decimal places as the recorded data.

For data reporting 3 or more numbers after the decimal point (i.e. urinalysis specific gravity), the descriptive statistics for mean, standard deviation, median, minimum, and maximum will all be reported to the same precision as the data was collected. For data reporting 2 numbers after the decimal point, the descriptive statistics for standard deviation will be reported as 3 numbers after the decimal place (same as the mean).

5.4.2 Frequency Distributions

Frequency distributions (count [n], percentage of subjects [%], and not reported) will be used to summarize categorical or qualitative variables. In general, the denominator for the percentage calculation will be based upon the total number of subjects in the study population for the treatment groups for that particular time point assessment. Records that are missing or not done will be displayed as “Not Reported” and will not be factored into the percentage calculation, unless otherwise specified. Percentages will be presented to a maximum of one number after the decimal place.

5.4.3 Safety Data Statistical Inference

All safety data summaries will use descriptive statistics, frequency distributions, and/or shift tables. No formal statistical testing will be performed with the safety data.

5.4.4 Efficacy and Pharmacodynamic Data Statistical Inference

5.4.4.1 P-values and Type I Error

P-values will be reported out and rounded off to 4 numbers after the decimal point (i.e. “0.#####). Any p-values that are > 0.9999 will be reported as “>.9999” in the tables. Any p-values that are < 0.0001 will be reported as “<.0001” in the tables. Unless otherwise specified, p-values will be tested using alpha at the 0.05 level. This pilot study is not formally powered to test any specific hypothesis; and, that should be taken into consideration for all statistical conclusions.

5.4.4.2 Paired *t*-test and Wilcoxon Signed-Rank Test

Testing for differences between treatment periods will be performed by using a 2-sided paired *t*-test, comparing pre and post values based on the analysis visits collected for particular pharmacodynamic and efficacy data stated in [Sections 9](#) and [10](#). The null hypothesis will be defined as the mean change from pre and post values is 0. Both the pre and post values must be non-missing in order to be included in the paired *t*-test comparison. Here is the SAS® code:

```
PROC TTEST DATA=ADAM;  
  /* where CHG# is the specific post-value – pre-value of interest */  
  VAR CHG#;  
RUN;
```

Additionally, the nonparametric Wilcoxon signed-rank test will be provided along with the 2-sided paired *t*-test. The null hypothesis will be defined as the median change from pre and post values is 0. Both the pre and post values must be non-missing in order to be included in the statistical comparison. Here is the SAS® code:

```
PROC UNIVARIATE DATA=ADAM;  
  /* where CHG# is the specific post-value – pre-value of interest */  
  VAR CHG#;  
RUN;
```

5.4.4.3 Frequency Distribution Tests

Frequency distributions that have two responses (i.e. yes/no) and compare two different treatment periods (i.e. NYX-2925 20 mg PO QD versus placebo) will use McNemar's exact test for reporting a p-value. This is referred to as a 2x2 table for dependent categorical data. Subjects will need to have both treatment period values as non-missing for the comparison. The 2x2 table must have less than 2 non-missing levels or the p-value will be considered non-calculable. Here is the SAS® code:

```
PROC FREQ DATA=ADAM;  
  WEIGHT COUNT;  
  /* where BEFORE and AFTER represent the 2 different treatment periods comparison */  
  TABLES BEORE*AFTER / AGREE;  
  EXACT MCNEM;  
  ODS OUTPUT MCNEMARSTEST=MCNEMARSTEST;  
RUN;
```

5.5 Analysis Visits

Analysis visits are determined based on the collected/derived data for the study that will be used for listings and statistical analyses. In some events, there may be differences in visits depending on the data used for statistical summaries and as a result analysis visits are defined. For example, data for

efficacy versus safety may have different methods for defining the analysis visits. The subsections below represent the analysis visits that will be used to support the analyses in this SAP.

In the event more than one record is collected/derived within an analysis visit, the non-missing record with the date closest to the target day will be selected. If there is a tie between two dates between the target date, then the first date will be used. If more than one non-missing record occurs on the same date, then the first planned scheduled result will be used.

Clinical laboratory tests will also consider lowest, highest, and most abnormal post-baseline results as additional analyses. More details are provided in [Section 12.2](#).

Week 1	Week 1	Day 1 to Week 1 Visit - 1
Week 2	Week 2	Week 1 Visit Day to Week 2 Visit - 1
Week 3	Week 3	Week 2 Visit Day to Week 3 Visit - 1
Week 4	Week 4	Week 3 Visit Day to Week 4 Visit - 1
Week 5	Week 5	Week 4 Visit Day to Week 5 Visit - 1
Week 6	Week 6	Week 5 Visit Day to Week 6 Visit - 1
Follow-Up/Week 7	Follow-Up (Week 7)	Week 6 Visit Day to Follow-Up Visit
N/A	After Follow-Up (Week 7) ^(a)	After the Follow-Up Visit

^(a) Screening and after Follow-Up (Week 7) values will be displayed in listings, but not included in summary tables.

5.6 Data Imputations

Standard methods described below will be used for imputing missing data and character values in numeric collected parameter data.

5.6.1 Character Values in Numeric Data

Characters such as “<, >, and/or =” may be included in some parameter data values that are supposed to be collected in a numeric format. This is most commonly seen in laboratory data. Analysis values for results with “<=” or “>=” will be analyzed with those characters stripped from the collected result (i.e. “<=1.030” = “1030” and “>=100” = “100”).

Analysis values with only “<” will be handled using these methods:

- For precision data collected with at least one number after the decimal point, the analysis value will be the numeric value minus 1 extra precision unit (i.e. “<0.1” = “0.09”).
- For whole numbers collected and the value reported as “<0” then the analysis value will be 0.
- For other whole numbers collected, the analysis value will be the numeric value minus 1.

Analysis values with only “>” will be handled using these methods:

- For precision data collected with at least one number after the decimal point, the analysis value will be the numeric value plus 1 extra precision unit (i.e. “>5.25” = “5.251”).
- For whole numbers collected, the analysis value will be the numeric value plus 1.

For listing purposes, the collected results will be displayed in the CSR listings and appendices (i.e. “<5.0” over “4.99”).

5.6.2 Missing Analysis Values

No missing analysis values will not be imputed for this study.

5.6.3 Missing or Partial Dates

Adverse Event Start Dates:

- Method 1 – Earliest Possible Start Date:
 - If any combination of the year, month, and/or day are missing then the start date will be set to the earliest possible date that is \geq to the screening date.
- Method 2 – Latest Possible Start Date:
 - If any combination of the year, month, and/or day are missing then the start date will be set to the latest possible date that is \leq to the latest possible adverse event end date. If the adverse event is ongoing after the final visit for the subject, then the final visit date will be used.

Prior/Concomitant Medications Start Dates:

- Method 1 – Earliest Possible Start Date:
 - If any combination of the year, month, and/or day are missing then the start date will be set to the earliest possible date that is \geq to the subject’s date of birth.
- Method 2 – Latest Possible Start Date:
 - If any combination of the year, month, and/or day are missing then the start date will be set to the latest possible date that is \leq to the latest possible medication end date. If the medication is ongoing after the final visit for the subject, then the final visit date will be used.

Adverse Event and Prior/Concomitant Medications End Dates:

- Method 1 – Earliest Possible End Date:
 - If any combination of the year, month, and/or day are missing then the end date will be set to the earliest possible date that is \geq to the earliest possible adverse event/medication start date.
- Method 2 – Latest Possible End Date:
 - If any combination of the year, month, and/or day are missing then the end date will be set to the latest possible date that is \leq to the subject's final visit date. If the adverse event/medication is ongoing after the final visit for the subject, then the final visit date will be used.

Medical History Disease Onset Dates:

- If year is missing, then the date will not be imputed.
- If both the month and day are missing, then the date will be imputed as July 1st with the year collected. However, if this imputed date is \geq to the screening date then the imputed date will be the screening date minus 1 day.
- If only the day is missing, then the date will be imputed as the 15th with the year and month collected. However, if this imputed date is \geq to the screening date then the imputed date will be the screening date minus 1 day.

5.7 Multiplicity Adjustments

No multiplicity adjustments will be made for this study.

5.8 By-Center Analyses

No formal by-center analyses is planned for this study.

5.9 Subpopulation Analyses

No formal subpopulation analyses are planned for this study.

6. Analysis Populations

Subjects who screened for the study, but were excluded from any of the analysis populations below will have the reasons why presented in a subject listing and frequency distribution tables.

6.1 Safety Population

All subjects who were dispensed study drug during the Day 1 (Baseline) visit and did not return all the study drug in their next visit will be in the safety population. It will be assumed that these subjects in the safety population have taken at least one dose of study drug. Subjects in the safety population will be used for all analyses of safety data and will be analyzed based on the actual treatment received within each treatment period in the study.

6.2 Efficacy Population

The efficacy population will be based on subjects included in the safety population and have at least one post-baseline visit after receiving NYX-2925 20 mg PO QD. Subjects in the efficacy population will be analyzed based on the planned treatment they were supposed to receive within each treatment period. The efficacy population will be the primary analysis population used for this study.

6.3 PP Population

The Per Protocol (PP) population will be based on all subjects in the efficacy population and the following criteria:

- Subjects first received Placebo for 2 weeks, then NYX-2925 20 mg PO QD for 2 weeks, and then NYX-2925 200 mg PO QD for 2 weeks;
- Subjects received the appropriate study drug for each treatment period;
- Subjects did not use any of the prohibited concomitant medications listed in Section 8.8 of the protocol;
- Subjects who have an overall NYX-2925 study drug treatment compliance between 80% and 125%;

Subjects in the PP population will be defined based on a review of the relevant data by the Sponsor prior to database lock and subjects may be excluded due to particular major protocol deviations.

Subjects in the PP population will be analyzed based on the planned treatment they were supposed to receive within each treatment period.

7. Disposition, Baseline, and Other Characteristics

All subjects will be summarized in the tables based each study treatment they were dispensed and received. The maximum strength study drug dose received, “Screen Failure” or “Not Treated” will be displayed in the subject listings.

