8.2. Investigational Product, Appearance, Packaging, and Labeling

Matching placebo capsules will contain only inactive ingredients listed previously.

Each bottle of IP will include 30 capsules of 10 or 100 mg NYX-2925, or matching placebo. The labels will include a kit number, capsule count, storage conditions, retest date, sponsor name, and investigational use statement. The sponsor will provide the investigative site with sufficient amounts of IP to conduct the study.

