8.1 Study Drug Accountability

Subjects will be dispensed study drug based on fixed treatment periods at visits Day 1 (Baseline), Week 2, and Week 4. In the event the subject comes in for an unscheduled visit prior to a weekly visit, they may be dispensed additional study drug. Additional study drug may be dispensed at any study visit or unscheduled visit if the subject will need study drug beyond the two week allotment

provided at Day 1, Week 2 and Week 4. Capsule strengths for NYX-2925 are 10 mg and 100 mg. Subjects will be instructed to take 2 capsules of investigational product once daily by mouth.

The following data will be collected and derived at each start and end to the study drug accountability treatment periods/visit intervals:

Parameter	Origin/Derivation
Capsules Dispensed Amount	CRF
Capsules Returned Amount	CRF
Expected Number of Capsules Taken	Derived: Date Returned – Date Dispensed + 1 (where the maximum would be 30 because 30 capsules are issued at each dispensing visit)
Estimated Number of Capsules Taken	Derived: Number of Capsules Dispensed Amount – Number of Capsules Returned Amount
Treatment Compliance (%)	Derived: $100 \times \frac{\text{Estimated Number of Capsules Taken}}{\text{Expected Number of Capsules Taken}}$ (rounded off by one number after the decimal point)

The Overall NYX-2925 Treatment Compliance (%) will be calculated as:

- $100 \times \frac{\sum (\text{Estimated Number of Capsules Taken at All Study Drug Return Visits After NYX-2925 20 mg or 200 mg PO QD was Dispensed})}{\sum (\text{Expected Number of Capsules Taken at All Study Drug Return Visits After NYX-2925 20 mg or 200 mg PO QD was Dispensed})}$ and rounded off by one number after the decimal point

A subject will be classified as being compliant with study drug administration if their calculated compliance by each treatment period and overall is between 80% and 125%, inclusive. Descriptive statistics will be summarized for treatment compliance by returning analysis visits Week 2 (Placebo), Week 4 (NYX-2925 20 mg PO QD), Week 6 (NYX-2925 200 mg PO QD), and Overall (NYX-2925 20 mg and 200 mg PO QD). The following categorical ranges will be summarized in a table for those same analysis visits and overall:

- <80%, 80-125%, >125%, and Not Reported

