Any study drug not returned during a subject's visit where study drug compliance is assessed will assume that all of that study drug was taken by the subject for analysis purposes. No adjustments will be made even if comments are documented on the CRF that stated lost samples were reported by the subjects. All study drug accountability comments will be provided in a subject listing. If a subject is lost to follow-up after being dispensed study drug, then the study drug returned and overall treatment compliance will be set to missing. Any unscheduled visits will be summarized within the study treatment periods based on the study drug dispensed (Placebo, NYX-2925 20 mg PO QD, or NYX-2925 200 mg PO QD).

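### PP entry in SAP 6.3 pools compliance over both NYX-2925 periods, unlike the by-period rule in SAP 8.1, and 8.1's expected capsule count needs correcting before any 80–125% rule can work

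*SAP*

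**What the plan says.** SAP 6.3 forms the PP set from the efficacy population by adding four conditions. The compliance condition covers "Subjects who have an overall NYX-2925 study drug treatment compliance between 80% and 125" per cent. It sets no limit for either dose period alone and none for placebo. Another condition asks that placebo, 20 mg and 200 mg were each received for 2 weeks. The sponsor settles membership in a review before database lock. Neither of these carries a capsule threshold.

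SAP 8.1 gives the pooled figure by formula ("The Overall NYX-2925 Treatment Compliance (%) will be calculated as"): the sum of capsules estimated as taken divided by the sum expected, over the 20 mg and 200 mg return visits together. The same section classifies a subject as compliant only "if their calculated compliance by each treatment period and overall is between 80% and 125%, inclusive".

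Three further conventions in SAP 8.1 matter here:

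- The expected count is "Derived: Date Returned – Date Dispensed + 1 (where the maximum would be 30 because 30 capsules are issued at each dispensing visit", although "Subjects will be instructed to take 2 capsules of investigational product once daily by mouth".
- For drug that is not returned, the plan "will assume that all of that study drug was taken by the subject for analysis purposes".
- On losses: "No adjustments will be made even if comments are documented on the CRF that stated lost samples were reported by the subjects". For a subject lost to follow-up, by contrast, returned drug and overall compliance are set to missing.

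**The concern.** SAP 5.1.6, 5.3 and 5.4.4.2 set up paired comparisons by period, so 20 mg and 200 mg each have their own change from Week 2 (placebo). A PP analysis of one dose should rest on subjects who took that dose as planned. A pooled figure cannot ensure this, because good adherence in one period makes up for poor adherence in the other. A subject can then be non-compliant under 8.1 and per-protocol under 6.3, and the SAP gives no reason for the difference.

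The capsule arithmetic in 8.1 feeds both rules. If the expected count is wrong, neither rule selects the subjects it is meant to select. If lost capsules count as swallowed, the by-period figures are inflated as well as the pooled one.

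**Working it through.** The plan states no figure for this point, so there is none to reproduce.

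**Inputs.** Two capsules once daily (SAP 8.1). Bottles of 30: "Each bottle of IP will include 30 capsules of 10 or 100 mg NYX-2925, or matching placebo" (Protocol 8.2). Two-week periods, with target days 14, 28 and 42 for Weeks 2, 4 and 6 (SAP 5.5.1). Limits of 80% and 125% (SAP 6.3 and 8.1).

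**Days per interval.** From Week 2 to Week 4, the SAP's day count is 28 − 14 + 1 = 15. From Week 4 to Week 6 it is 42 − 28 + 1 = 15. Fourteen dosing days need 2 × 14 = 28 capsules; fifteen need 30.

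**Pooled rule at two capsules a day.** Overall % = 100 × (taken in period 1 + taken in period 2) / (expected in period 1 + expected in period 2).

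| Expected per period | Most that can be counted | Example that passes | Overall | Lower period |
|---|---|---|---|---|
| 28 | 28 | 28 + 17 | 45/56 = 80.4% | 17/28 = 60.7% |
| 30 | 30 | 30 + 18 | 48/60 = 80.0% | 18/30 = 60.0% |
| 30 | 28 | 28 + 20 | 48/60 = 80.0% | 20/30 = 66.7% |
| 28 | 30 | 30 + 15 | 45/56 = 80.4% | 15/28 = 53.6% |

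Each example is the lowest single-period compliance that still passes 6.3 on that row's assumptions. Each fails the by-period test in 8.1.

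**With a by-period limit.** The lowest passing count becomes 23 of 28 (82.1%; 22/28 = 78.6% fails) or 24 of 30 (80.0%).

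**The formula as printed.** Expected is 15 per period and 30 over both.

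- Full adherence scores 28/15 = 186.7% in each period and 56/30 = 186.7% overall. It fails as above 125%.
- The passing range is 0.80 × 30 = 24 to 1.25 × 30 = 37.5, that is 24 to 37 of 56 capsules.
- A subject with 28 capsules in one period and none in the other scores 28/30 = 93.3% and passes.

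The maximum of 30, explained by 30 capsules being issued, makes sense in capsules at two a day (2 × 15 = 30). It would never bind on a two-week count of days. A factor of two was probably intended.

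**Lost capsules.** A subject takes 14 of 28 capsules (50%), loses the rest of the bottle and returns none. Estimated taken is 30 − 0 = 30. At two a day the period scores 30/30 = 100% with 15 days counted, or 30/28 = 107% with 14. Both lie inside the limits, and the score would be the same had no capsule been taken. A by-period rule does not cure this.

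**The case against.** The strongest reply is that 6.3 does not borrow the classification in 8.1. It names a different quantity with its own formula, and two definitions for two purposes can be a deliberate choice. This stands so far as it goes: the sections differ, and neither is impossible to apply. It does not explain why a pooled figure suits comparisons made dose by dose.

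The second reply is that other safeguards exist: the two-week condition, the pre-lock sponsor review, compliance tabulated at Weeks 2, 4 and 6, and a listing of accountability comments. These could lead to exclusion of such a subject, but none sets a numeric limit. SAP 13.1 also allows PP exclusions after lock, and Protocol 8.7 leaves sponsor personnel unblinded, so a fixed rule is preferable to discretion.

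A reader might infer more than the documents support:

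- *That the lost-capsule rule contradicts 8.1.* It is part of 8.1.
- *That a lost bottle always keeps an under-dosed subject in PP.* That needs the two-a-day denominator. As printed, the period scores 30/15 = 200%; with 28 capsules in the other period the pooled figure is 58/30 = 193%, and the subject is excluded.
- *That PP results are shown to be biased toward zero.* Dilution is the expected direction if effect depends on exposure, but no frequency of uneven adherence is given and the efficacy sections of the SAP are blacked out. Imaging falls in the last week of each period, so early missed doses may matter little.
- *That omitting placebo compliance lets under-dosed subjects in.* A placebo limit would serve consistency with 8.1; it does not address under-dosing with NYX-2925.

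**Conclusion.** The point holds as a minor one. On a two-capsule-a-day count, the 6.3 rule passes subjects with compliance as low as about 60% in one dose period (54% to 67% across the counting assumptions shown), whom 8.1 would call non-compliant. As printed, the expected count in 8.1 excludes fully adherent subjects at about 187%, so it must be settled before either rule is usable. The lost-capsule convention is a separate weakness, which can show a mostly missed period as about 100%.

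The figures assume 14-day dosing periods and one 30-capsule bottle per period; visit windows and extra dispensing would shift them slightly. Passing here means passing the compliance condition only. With about 24 subjects planned, one misclassified subject is at least 1/24 = 4% of the PP set. The consequence is limited, because SAP 6.2 makes the efficacy population primary. The documents do not establish that any PP estimate would be materially changed.

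**What to change.** 1. In SAP 8.1, first correct the expected count to 2 × the number of dosing days in the interval, and state how the dispensing and return days are counted.
2. In SAP 6.3, replace the pooled condition with 80–125% in each NYX-2925 period being compared. Add the placebo period if consistency with 8.1 is intended.
3. In SAP 8.1, where loss of capsules is documented, set that period's compliance to missing, as the section already does for overall compliance in subjects lost to follow-up. Alternatively, check the period at the pre-lock PP review against the missed-dose data that SAP 5.1.1 says are captured and the noncompliance recorded under Protocol 8.6.

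These are wording and programming changes and need no new data. The cost is a slightly smaller PP set, and some loss reports cannot be verified. The order matters: a by-period limit applied to the printed formula would remove every fully adherent subject.
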